## **9.2 Sources and strategy to collect data**

Based on current experience during product development as well as information known to be available regarding other similar products, the following strategies are to be used to locate and gather all relevant information:

- (i) Initial general searches to establish the parameters used to determine the acceptability of the DUE benefit-risk ratio, and to identify early clinically relevant information pertinent to the DUE and its intended use. Preliminary general searches also contribute to elaborate an accurate PICO strategy for the literature review, and to establish more specific search terms with the purpose of obtaining state-of-the-art relevant data.
- (ii) Searches of peer-reviewed scientific literature to establish the scientific basis, technical and clinical requirements as related to the identified clinical need, clinical conditions, standard of care, state of the art, similar devices, and alternative treatment methods.
- (iii) Search and review of background and clinical experience as related to similar devices, including clinically relevant information coming from post-market surveillance and/or post-market clinical follow-up.
- (iv) Search of scientific literature with published results of clinical investigation(s) and other studies to determine:
  - a. Possible benefits
  - b. Possible risks, side-effects and harm that may have been due to the DUE or similar devices
  - c. Safety information as related to the DUE or similar devices.
- (v) (In-house / Unpublished) Clinical investigation report(s) as related to the device concerned.

Strategy (i) will be used to define the clinical evaluation scope, the regulatory strategy, and the framework for the design of the consequent literature searches. These preliminary State of the Art Results should drive the Safety and Performance objectives for the DUE.

Dilemma Solutions S.L.	CHAPTER 06-1C	TD01-06-1C Ver.: 01 2025/03/03
	CLINICAL EVALUATION PLAN (CEP)	Page 17 of 38

Strategies (ii) and (iii) will be used to establish the clinical aspects and characteristics for which ample scientific, technical and/or clinical data are believed to be already available.

Strategy (iv) will be used to locate clinically relevant data sets for the device concerned or for reference devices that may be demonstrated to be equivalent.

Strategy (v) will be used if the device itself has undergone clinical investigation, clinical trial, or other clinical study.

The following sources shall be considered:

- Scientific databases: PubMed
- Systematic review databases: Cochrane library
- Manual searches (internet searches, vigilance databases, non-published data and Citations referenced in scientific literature).

The clinical evaluation for the device under evaluation is planned, conducted, and documented according to article 61 and Annex XIV part A of the MDR and applicable MDCG guidelines. Nevertheless, the MEDDEV 2.7/1 (Rev.4 of June 2016) is useful to structure the clinical evaluation, to establish an appraisal plan and to establish the different stages of the Clinical Evaluation process (see figure 2 below).

#### **Stage 0: Clinical Evaluation Scoping and Planning (as set out in this document)**

**Stage 1: Identification of clinical data relevant to the device and its intended use (as described above), and any gaps in clinical evidence, through a systematic scientific literature review.** The details of the literature review to be conducted are established in a Literature Search Protocol. This protocol defines the specific search terms and search algorithms to be applied (as determined by current knowledge of the device, the conditions of use, intended use, indications for use), inclusion and exclusion criteria to be applied to articles and data sets found and to determine which datasets can only be considered as contribution to information about the state of the art and which datasets meet the definition of “clinical data” and hence can be routed to the appraisal stage. If data pertaining to a similar device is considered, clinical, biological, and technical equivalence to the device under evaluation must first be demonstrated with sufficient explanation and rationale for any gaps found. Search terms and search algorithms are defined so that the search is repeatable, thorough, objective, and comprehensive (depth and extent are proportionate and appropriate to the nature classification, intended purpose and risks of the device) taking into account both favourable and unfavourable data.

Dilemma Solutions S.L.	CHAPTER 06-1C	TD01-06-1C Ver.: 01 2025/03/03
	CLINICAL EVALUATION PLAN (CEP)	Page 18 of 38

**Stage 2: Appraisal of all clinical data by evaluating their suitability for establishing the safety and performance of the device.** The Literature Search Protocol also contains the appraisal plan and methods to be applied to assess all relevant clinical data by evaluating their suitability to establish the safety and performance of the DUE. The results of the execution of the Literature Search Protocol shall be documented in the Literature Search Report. A summary with the most relevant results and conclusions shall be extracted to the Clinical Evaluation Report.

[figure not shown]
**Stage 3: Analysis of all relevant “clinical data” in order to reach conclusions about the safety and performance of the device, including its clinical benefits.**

Appraised clinical data is analysed to determine if there is “sufficient clinical evidence” to conclude that the device is safe and achieves its intended benefits. The level of clinical evidence to be attained is specified in Section 13 below. The analysis contemplates relevant information collected concerning clinical benefits that are confirmed, quantification of risk frequency and severity as well as confirmation of the effectiveness of risk control measures, a qualitative and, if possible, quantitative determination of the benefit-risk ratio (e.g., marginally positive versus clearly positive) Any missing data or gaps in clinical data are identified. If it cannot be concluded that sufficient clinical evidence is available, then additional clinical data must be generated, e.g. through additional literature searching and/or through specific clinical investigations in accordance with the clinical development plan to address outstanding gaps and/or issues.

**Stage 4: Clinical Evaluation Report. PMS Plan. PMCF Plan.**

Results of the previous steps along with the conclusions concerning the availability of sufficient clinical evidence are documented, reviewed, and approved in the Clinical Evaluation Report. Ongoing steps to continuously update the clinical evaluation are set out in the PMS Plan and PMCF Plan.

Dilemma Solutions S.L.	CHAPTER 06-1C	TD01-06-1C Ver.: 01 2025/03/03
	CLINICAL EVALUATION PLAN (CEP)	Page 19 of 38

**Figure 2.** Stages of Clinical evaluation according to MEDDEV 2.7/1 (Rev.4)

### **9.3 Preliminary systematic review**

A pilot scientific literature review was performed to identify initial State of the Art clinical data relevant to the device safety and performance objectives and its intended use, as detailed below.

Based on the results and outcomes from this preliminary search, the full PICO strategy, search terms and search algorithms are established and detailed in the Literature Search Protocol.

- **Search details:** "clinical decision support systems"[Title] NOT artificial intelligence / **Filters:** Review [article type], Systematic Review [article type], Humans [species] → 135 results

Search query: ("clinical decision support system"[Title]) AND ((y\_5[Filter]) AND (humans[Filter]))

- **Search details:** "clinical decision support systems"[Title] NOT artificial intelligence AND recommendations / *No filters applied* → 84 results

Search query: ("clinical decision support systems"[Title] NOT ("artificial intelligence"[MeSH Terms] OR ("artificial"[All Fields] AND "intelligence"[All Fields]) OR "artificial intelligence"[All Fields])) AND ("recommend"[All Fields] OR "recommendable"[All Fields] OR "recommendation"[All Fields] OR

Dilemma Solutions S.L.	CHAPTER 06-1C	TD01-06-1C Ver.: 01 2025/03/03
	CLINICAL EVALUATION PLAN (CEP)	Page 20 of 38

"recommendation s"[All Fields] OR "recommendations"[All Fields] OR "recommended"[All Fields] OR "recommending"[All Fields] OR "recommends"[All Fields]

- **Search details:** "ischemic heart disease"[Title] / *Filters:* in the last 5 years [publication date], Review [article type], Systematic Review [article type], Humans [species] → 142 results

Search query: ("ischemic heart disease"[Title]) AND ((y\_5[Filter]) AND (review[Filter] OR systematicreview[Filter]) AND (humans[Filter]))

- **Search details:** "valvular heart disease"[Title] / *Filters:* in the last 5 years [publication date], Review [article type], Systematic Review [article type], Humans [species] → 91 results

Search query: ("valvular heart disease"[Title]) AND ((y\_5[Filter]) AND (review[Filter] OR systematicreview[Filter]) AND (humans[Filter]))

- **Search details:** "clinical decision support system"[Title] AND (side effects OR adverse effects OR clinical risks) / *No filters applied* → 217 results

Search query: "clinical decision support system"[Title] AND ("adverse effects"[MeSH Subheading] OR ("adverse"[All Fields] AND "effects"[All Fields]) OR "adverse effects"[All Fields] OR ("side"[All Fields] AND "effects"[All Fields]) OR "side effects"[All Fields] OR ("adverse effects"[MeSH Subheading] OR ("adverse"[All Fields] AND "effects"[All Fields]) OR "adverse effects"[All Fields]) OR (( "ambulatory care facilities"[MeSH Terms] OR ("ambulatory"[All Fields] AND "care"[All Fields] AND "facilities"[All Fields]) OR "ambulatory care facilities"[All Fields] OR "clinic"[All Fields] OR "clinic s"[All Fields] OR "clinical"[All Fields] OR "clinically"[All Fields] OR "clinicals"[All Fields] OR "clinics"[All Fields]) AND ("risk"[MeSH Terms] OR "risk"[All Fields] OR "risks"[All Fields])))

The following articles were considered relevant to reach the objective of this search. Another approach used to identify relevant information for the clinical evaluation of the DUE was the manual search used as a supplemental path to find the following additional relevant articles. Copies of the selected articles are gathered attached to the present document.

2. Sutton, R. T., Pincock, D., Baumgart, D. C., Sadowski, D. C., Fedorak, R. N., & Kroeker, K. I. (2020). An overview of clinical decision support systems: benefits, risks, and strategies for success. *NPJ digital medicine*, 3, 17. <https://doi.org/10.1038/s41746-020-0221-y>
3. Kwan, J. L., Lo, L., Ferguson, J., Goldberg, H., Diaz-Martinez, J. P., Tomlinson, G., Grimshaw, J. M., & Shojania, K. G. (2020). Computerised clinical decision support systems and absolute improvements in care: meta-analysis of controlled clinical trials. *BMJ (Clinical research ed.)*, 370, m3216. <https://doi.org/10.1136/bmj.m3216>

Dilemma Solutions S.L.	CHAPTER 06-1C	TD01-06-1C Ver.: 01 2025/03/03
	CLINICAL EVALUATION PLAN (CEP)	Page 21 of 38

4. Jensen, R. V., Hjortbak, M. V., & Bøtker, H. E. (2020). Ischemic Heart Disease: An Update. *Seminars in nuclear medicine*, 50(3), 195–207. <https://doi.org/10.1053/j.semnuclmed.2020.02.007>

## 10. Methods for assessment of clinical safety

Clinical safety concerns, including known residual risks and side-effects of medical device software, shall be identified from Risk analysis/Risk assessment, vigilance/adverse events databases and published scientific literature. Specific benefit-risk assessment includes the parameters described in Section 11 of the present report.

Identification of initial data concerned to clinical safety shall be identified through consultation of vigilance and/or adverse-events databases for similar devices. This strategy is also described in section 9 of the present document.

Specific databases that shall be used for clinical safety data identification are:

- Agencia Española de Medicamentos y Productos Sanitarios (AEMPS) – Medical Devices Alerts
- Medicine and Healthcare Products and Regulatory Agency (MHRA) – Alerts and recalls for drugs and medical devices
- FDA Medical Devices Recalls
- FDA Total Product Life Cycle (TPLC)
- FDA Manufacturer and User Facility Device Experience (MAUDE)

The following sections detail the potential specific residual clinical risks and the foreseeable side effects related to the use of the device under evaluation that shall be addressed in the Clinical Evaluation and supported with clinical data.

As stated previously, the device has no special characteristic or novel features. However, residual risks will be addressed in the device risk management documentation to manage any special performance or safety concerns.

Clinical safety of the DUE will be determined:

Dilemma Solutions S.L.	CHAPTER 06-1C	TD01-06-1C Ver.: 01 2025/03/03
	CLINICAL EVALUATION PLAN (CEP)	Page 22 of 38

- Indirectly on the basis of software verification and validation.
- Through the assessment of the characteristics of the finished device and fulfilment of technical specifications.
- Through review and assessment of clinical data assessing the safety and performance of similar / equivalent devices.
- Through review and assessment of incidents, adverse events, or other relevant safety reports for similar / equivalent devices.

In particular, information concerning potential specific residual clinical risks and the foreseeable side effects related to the use of the device under evaluation that shall be addressed in the Clinical Evaluation and supported with clinical data are gathered in the following sub-sections.

#### **10.1. Residual risks**

Residual risks were analysed and addressed following the Risk Management Plan. Risks that are relevant during clinical use and residual risks are listed below and shall be considered when searching for relevant clinical data.

Relevant risks during clinical use and residual risks are listed below and shall be considered when searching for pertinent clinical data to the DUE.

Risk ID	Risk	Description
2	Misdiagnosis caused by product's error	The user makes a clinical decision based on wrong recommendations.
3	Misdiagnosis caused by user's errors	The output data given by the software is not adequate for the patient. The user makes a clinical decision based on wrong recommendations.
4	Patient's privacy and data security	The output data given by the software is not adequate for the patient due to the corruption of patient's data. The user makes a clinical decision based on wrong recommendations.

#### **10.2. Foreseeable side-effects**

No side-effects have been identified for this device.

### **11. Basis to determine the acceptability of the benefit-risk ratio**

Dilemma Solutions S.L.	CHAPTER 06-1C	TD01-06-1C Ver.: 01 2025/03/03
	CLINICAL EVALUATION PLAN (CEP)	Page 23 of 38

Naevia Medical is a clinical decision support software (CDSS) that, based on clinical input data (history, symptoms, complementary test data...) of adult patients with heart disease, provides healthcare professionals with prioritized, justified and referenced recommendations and knowledge suggestions related to diagnosis and/or treatment (recommended tests, medications,...).

The main clinical benefit obtained with the DUE is the following:

- Direct clinical benefit to provide healthcare professionals with recommendations and suggestions for knowledge related to diagnosis, prognosis and/or treatment.

The main complications associated with the use of product category are the following:

- Misdiagnosis caused by product's error.
- Misdiagnosis caused by user's errors.
- Patient's privacy and data security.

The risk-benefit ratio is favorably justified when the benefits in improved quality of care, increased appropriate recommendations and decreased inappropriate recommendations outweigh the risks associated with the use of CDSS. This requires careful knowledge modelling, correct implementation, constant monitoring and continuous updating. Acceptance of the system by clinical users is crucial and must be ensured through appropriate training, support and participation in system improvement.

Clinical benefits and possible complications or side effects related to the use of naevia Medical will be further investigated and assessed in the planned literature searches and included in the Clinical Evaluation Report (see Benefit-Risk Analysis in section 5 of the Technical Documentation).

Based on the state of the art in medicine, the acceptability of the DUE benefit-risk ratio for the indications mentioned above, depends on clinical safety and performance parameters and outcomes as listed below.

Dilemma Solutions S.L.	CHAPTER 06-1C	TD01-06-1C Ver.: 01 2025/03/03
	CLINICAL EVALUATION PLAN (CEP)	Page 24 of 38

**Table 1 – Naevia Medical – Indicative List of Clinical Safety and Performance Parameters and Quantitative Measures**

Parameter / Outcome	Quantitative Measure of Performance	Source / Level of Evidence Required	
Performance of Naevia medical to provide healthcare professionals with recommendations and suggestions for knowledge related to diagnosis, prognosis and/or treatment			
Software enables to provide recommendations and suggestions for knowledge related to diagnosis, prognosis and/or treatment	
Goal: all basic key characteristics of CDSS are supported and all supported characteristics work correctly and as expected.
 
[references to sources]
 
*EN ISO 62304 – Medical device software – Software life-cycle processes
 
EN 82304 – Health Software – Part 1: General requirements for product Safety
	Preclinical	
Accepted if using the system functions and features, users are able to get recommendations and suggestions for knowledge related to diagnosis, prognosis and/or treatment.
 
 
- V&V per EN ISO 62304 and install validation. All tests provide recommendations and suggestions and thus CDSS is verified by all tests.
 
- V&V per EN 82304 and install validation. All tests provide recommendations and suggestions and thus CDSS is verified by all tests.
 
- Usability testing of the software by representative users to successfully provides recommendations and suggestions for knowledge related to diagnosis, prognosis and/or treatment.
 

		Clinical	
Accepted if system features cover user needs for getting recommendations and suggestions for knowledge related to diagnosis, prognosis and/or treatment aligned with the tools required for medical diagnosis support and using the system functions and features, users successfully use CDSS to make clinical decisions regarding diagnosis, prognosis and/or treatment.
 
 
- V&V per EN ISO 62304 and install validation. All tests provide recommendations and suggestions and thus CDSS is verified by all tests*.
 
- V&V per EN 82304 and install validation. All tests provide recommendations and suggestions and thus CDSS is verified by all tests.
 

Dilemma Solutions S.L.	CHAPTER 06-1C	TD01-06-1C Ver.: 01 2025/03/03
	CLINICAL EVALUATION PLAN (CEP)	Page 25 of 38

	43(7), https://doi.org/10.1093/eurheartj/ehab395	561-632.		
Appropriate recommendations	Increase the number of appropriate recommendations by a factor of three	Clinical	-	An observational study consisting on a clinical validation of a CDSS applied to retrospective clinical cases of cardiac patients with valvular heart disease, shall confirm an increase in the number of appropriate recommendations by a factor of three over the recommendations generated with conventional management without the support system.
Inappropriate recommendations	Reduction of inappropriate recommendations	Clinical	-	An observational study consisting on a clinical validation of a CDSS applied to retrospective clinical cases of cardiac patients with valvular heart disease, shall confirm that Naevia medical, compared to conventional management, is able to significantly decreased the number of inappropriate and missing recommendations in all the domains analyzed.

Dilemma Solutions S.L.	CHAPTER 06-1C	TD01-06-1C Ver.: 01 2025/03/03
	CLINICAL EVALUATION PLAN (CEP)	Page 27 of 38

Concordance between expert evaluators	Professionals agreement [reference to sources]  *Joshi, A., S. Kale, S. Chandel and D. K. Pal (2015). "Likert Scale: Explored and Explained." Current Journal of Applied Science and Technology 7: 396-403.	Clinical	
 
- The panel's agreement with the CDSS was very high, with a mean Likert scale score above 4 in all domains (STD: 4.53, LTD: 4.68, CMT: 4.58, ITI: 4.62). The probability of strongly agreeing was significantly higher than the probability any of the other categories (z.ratio (5 1)= 30.88, p-value< 0.001, z.ratio (5 2)= 31.67, p-value < 0.001, z.ratio (5 3) = 30.21, p-value< 0.001, z.ratio (5 4)= 22.54, p-value< 0.001).
 
-
 

Safety of Naevia medical			
Misdiagnosis caused by product's error	Incidence with SW System not > documented incidence with similar devices	Clinical	
 
- Incidents and adverse events (if any) related to the DUE and linked to misdiagnosis caused by product's error in the DUE do not result in serious harm, injury or impairment to the patient. 
 
o No serious clinical complications or other effects linked to misdiagnosis caused by product's error in the DUE are observed in the clinical studies and registries performed with the DUE.
 
 
 
- Incidents and adverse events (if any) related to the DUE and linked to misdiagnosis caused by product's error in the DUE do not frequently result in serious harm, injury or impairment to the patient. 
 
o Output from ongoing review of incidents and adverse events (if any) related to the DUE and similar devices confirms a low incidence of clinical complications or other effects linked to misdiagnosis caused by product's error.
 
 
 

	Incidence with SW System not > documented incidence with similar devices	Clinical	
 
- Incidents and adverse events (if any) related to the DUE and linked to misdiagnosis caused by user's error in the DUE do not result in serious harm, injury or impairment to the patient.
 

Dilemma Solutions S.L.	CHAPTER 06-1C	TD01-06-1C Ver.: 01 2025/03/03
	CLINICAL EVALUATION PLAN (CEP)	Page 28 of 38

Misdiagnosis caused by user's errors			
 
○ No serious clinical complications or other effects linked to misdiagnosis caused by user's error in the DUE are observed in the clinical studies and registries performed with the DUE.
 

			
 
- Incidents and adverse events (if any) related to the DUE and linked to misdiagnosis caused by user's error in the DUE do not frequently result in serious harm, injury or impairment to the patient. 
 
○ Output from ongoing review of incidents and adverse events (if any) related to the DUE and similar devices confirms a low incidence of clinical complications or other effects linked to misdiagnosis caused by user's error in these systems.
 
 
 

Patient's privacy and data security	Incidence with SW System not > documented incidence with similar devices	Clinical	
 
- Incidents and adverse events (if any) related to the DUE and linked to patient's privacy and data security issues in the DUE do not result in serious harm, injury or impairment to the patient. 
 
○ No serious clinical complications or other effects linked to patient's privacy and data issues in the DUE are observed in the clinical studies and registries performed with the DUE.
 
 
 

			
 
- Incidents and adverse events (if any) related to the DUE and linked to patient's privacy and data security issues in the DUE do not result in serious harm, injury or impairment to the patient. 
 
○ Output from ongoing review of incidents and adverse events (if any) related to the DUE and similar devices confirms a low incidence of clinical complications or other effects linked to patient's privacy and data security issues in these systems.
 
 
 

Dilemma Solutions S.L.	CHAPTER 06-1C	TD01-06-1C Ver.: 01 2025/03/03
	CLINICAL EVALUATION PLAN (CEP)	Page 29 of 38

Recommendations that could lead to a serious adverse event	
Naevia medical does NOT provide recommendations that could lead to a serious adverse event shall be identified as patient safety risks, including:
 
 
- Possibility of death.
 
- The need for a medical or surgical intervention that would not otherwise be necessary.
 
- Omission of critical recommendations that could adversely affect the patient's prognosis
 
	Clinical	
 
- An observational, study consisting on a clinical validation of a CDSS applied to retrospective clinical cases of patients with valvular heart disease; must determine whether Naevia medical, when faced with real clinical cases, issues inappropriate recommendations that may represent a risk to patient safety. Recommendations that could lead to a serious adverse event shall be identified as patient safety risks, including: 
 
o Possibility of death.
 
o The need for a medical or surgical intervention that would not otherwise be necessary.
 
o Omission of critical recommendations that could adversely affect the patient's prognosis.
 
 
 

---	---	----------	---

Dilemma Solutions S.L.	CHAPTER 06-1C CLINICAL EVALUATION PLAN (CEP)	TD01-06-1C Ver.: 01 2025/03/03
		Page 30 of 38

The benefit-risk balance is focused on the assessment of:

- History of safe use of similar devices.
- The residual clinical risks when using the device as intended by the manufacturer should not be higher than those already described in the literature and post-commercialization experience for similar devices already available on the market.
- The preclinical and clinical studies performed for the DUE following the parameters included in the applicable standards are available and will support the safety profile of the DUE.
- A market experience search regarding the history of safe use of similar devices will be performed and will be detailed in the Literature Search Report in order to identify the possible clinical risks arising from the use of similar products that are already available in the market.

The clinical benefits expected by the use of the DUE are detailed in Section 7 of this Clinical Evaluation Plan.

Possible risks arising from the use of the device have been identified in the Risk Management Report and the benefit/risk analysis related are detailed in sub-section 10.1 of this Clinical Evaluation Plan.

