### Main clinical investigation

Title	Clinical validation study of naevia medical, a decision support tool for valvular heart disease
Registration number	ClinicalTrials.gov ID NCT06392464
Start and End	2024
Publication	Pending
Design	pre-test-post-test of a randomly assigned group, using a longitudinal repeated measures approach and retrospective validation
Duration	3 months
Centres	Instituto de Investigación Sanitaria de Santiago de Compostela (IDIS)
Sponsor	DILEMMA SOLUTIONS SL
Main objective	Demonstrate that the use of the naevia medical CDSS significantly increases appropriate recommendations based on clinical practice guidelines, and decreases the number of inappropriate recommendations received by the patient, compared to conventional management.
Device investigation under	Naevia medical
Number of participants	101

Dilemma Solutions S.L.	CHAPTER 06-1C CLINICAL EVALUATION PLAN (CEP)	TD01-06-1C Ver.: 01 2025/03/03
		Page 33 of 38

Title	Clinical validation study of naevia medical, a decision support tool for valvular heart disease	
Inclusion criteria	
Retrospective clinical retrospective cases of patients with valvular heart disease will be selected in a stratified randomised manner from among:
 
 
(i) patients presented at a medical-surgical session.
 
ii) patients from the monographic consultation of valvopathies.
 
 
Inclusion criteria:
 
 
- Clinical cases of patients randomly selected from among those presented during the year 2022 in medical-surgical session with the main diagnosis of aortic valvular stenosis, aortic insufficiency, mitral stenosis and mitral insufficiency (greater than moderate grade). Randomisation will be stratified ensuring that 50% come from the medical-surgical session.
 
- Clinical cases of patients randomly selected from clinical records of the Valvopathy Consultation seen in 2022 with the main diagnosis of aortic stenosis, aortic insufficiency, mitral stenosis and mitral insufficiency (major degree).
 
mitral regurgitation (greater than moderate grade). Randomisation will be stratified by ensuring that at least 40% of patients have aortic valve disease and 20% have mitral valve disease.
 
- Age <math>\geq 18</math> years.
 
	

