	
(1.9%) and the number of wrong answers decreased from 228 to 208 (8.7%) (<math>p=0.29</math>). External validation phase 2: 21 additional cases were evaluated by 4 experts (2 with, 2 without CDSS) and 4 non-experts (2 with, 2 without CDSS). The answers showed low concordance both inter and intra group, with and without CDSS (<math>\kappa < 5</math> for all evaluated answers).

Protocol reference	TD01-06-1C-06-01 CIP_2021-2-19-HCUVA

Additionally, Naevia Medical's platform has been or is being used in other significant registries, such as:

- The "REDMIO20: Spanish Registry of Dilated Cardiomyopathy due to RBM20 Gene Mutation," a multicenter registry coordinated by [name] from the Salamanca University Assistance Complex, which included 168 cases up to December 11, 2023.
  - o Protocol reference: *TD01-06-1C-06-03 CIP\_REDPMIO*
- The "PROceso asistencial integrado de Estenosis Aórtica grave Sintomática (PROCEAS)" 2020/405 registry, led by [name] from the Santiago de Compostela University Clinical Hospital, with 991 cases of aortic stenosis registered up to December 11, 2023.
  - o Protocol reference: *TD01-06-1C-06-04 CIP\_PROCEAS*

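### The comparative safety measure in Table 1 has no confidence bound or denominator, so for rare events and few uses it can be met through lack of data

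*Protocol*

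**What the plan says.** Protocol Section 11 says that acceptability of the benefit-risk ratio depends on the parameters in Table 1. For misdiagnosis from product error, misdiagnosis from user error, and privacy and data security, the measure is "Incidence with SW System not > documented incidence with similar devices". The list that closes the section says in its second bullet that residual clinical risks "should not be higher than those already described in the literature and post-commercialization experience for similar devices".

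The reference incidence is not given: "A market experience search regarding the history of safe use of similar devices will be performed", with details left to the Literature Search Report. The only hint of its size is in the acceptance text, where ongoing incident review "confirms a low incidence of clinical complications or other effects linked to misdiagnosis caused by product's error".

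The same rows carry a second condition, that no serious complications linked to the risk "are observed in the clinical studies and registries performed with the DUE". A fourth safety row covers recommendations that could lead to a serious adverse event.

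On denominators, the main investigation (Section 14) gives "Number of participants 101". Two registries that use the platform are also listed, one "which included 168 cases up to December 11, 2023" and one "with 991 cases of aortic stenosis registered up to December 11, 2023".

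The SAP analyses counts of appropriate, inappropriate and missing recommendations with a Wilcoxon signed-rank test, and collects Likert agreement. It has no analysis of safety incidence.

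**The concern.** A statement that one incidence is not greater than another needs a rule for how much data is enough. Without a bound, the natural reading is that the measure is met when the observed rate does not exceed the documented one. For a rare event and a small denominator the expected count is close to zero, so zero is a likely observation whether the device matches its comparators or is somewhat worse. The less the device has been used, the easier the measure then is to meet.

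This is separate from the condition on serious complications, and it would remain even if every case were a real use with full follow-up. At stake is the comparative conclusion that residual risk is no higher than with similar devices.

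**Working it through.** **Inputs**
- Reference incidence p0: not in the documents. Assumed here from 0.1% to 5%.
- n = 101: main clinical investigation, Section 14. No derivation, alpha, power or margin accompanies it, so there is no plan figure to reproduce.
- n = 1389: a generous sensitivity case from the cases listed in Section 14. It is 101 (main study) + 60 (hypertrophic cardiomyopathy, internal validation) + 69 (colorectal screening) + 168 + 991 (registries).
- True incidence twice p0: chosen for illustration.

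**Rule tested.** The plan states no decision rule. Read literally as a point-estimate comparison, the measure is met if X/n ≤ p0, that is X ≤ floor(n·p0), with X ~ Binomial(n, true incidence).

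**Chance of meeting the measure, n = 101**

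| Assumed p0 | Events allowed | True incidence = p0 | True incidence = 2·p0 |
|---|---|---|---|
| 0.1% | 0 | 90% | 82% |
| 0.5% | 0 | 60% | 36% |
| 1% | 1 | 73% | 40% |
| 2% | 2 | 67% | 23% |
| 3% | 3 | 64% | 14% |
| 5% | 5 | 61% | 5% |

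Example: at p0 = 0.1%, no events are allowed and (1 − 0.002)^101 = 0.817. The rise from 36% to 40% comes from rounding n·p0 down to a whole count. The third column shows that the bare comparison also turns away a device exactly as safe as its comparators in 27–40% of trials for p0 from 0.5% to 5%.

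**Same calculation, n = 1389, true incidence 2·p0**
- p0 = 0.1% (1 event allowed): 23.5%
- p0 = 0.2% (2 allowed): 8.5%
- p0 = 0.5% (6 allowed): 1.5%
- p0 = 1% (13 allowed): 0.1%

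**What zero events exclude.** The one-sided 95% exact upper bound is 1 − 0.05^(1/n). For 0/101 this is 2.9%; for 0/1389 it is 0.22%.

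**Effect of the serious-complication condition.** If every event were serious, passing would need zero events. At n = 101 and twice p0 the chance is (1 − 0.02)^101 = 13% at p0 = 1% and (1 − 0.04)^101 = 1.6% at 2%. Below about 1% nothing changes, because floor(101·p0) is already 0.

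**Is 101 a denominator at all?** The SAP describes a panel of three experts reviewing, retrospectively, the management of the included cases. Neither document describes follow-up of incidents after the device was used in those cases. They may therefore yield no misdiagnosis incidence, and the n = 101 figures show how the rule behaves, not what this study will observe.

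**The case against.** The measure does not stand alone. It shares its rows with the condition on serious complications and with ongoing incident review, and there is a fourth safety row. Table 1 is titled indicative, and the closing list in Section 11 describes what the assessment focuses on, not a pass/fail test. Stage 3 in Section 9.2 asks for risk frequency to be quantified and gaps identified, and requires more data if evidence is insufficient. The reference incidence, and perhaps denominators, may appear in the Literature Search Report, the risk management documents or the separate study protocol, which are not among the documents reviewed.

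Much of this stands. A reader might infer that safety as a whole is accepted on this comparison; the other conditions show otherwise. A reader might infer that a device with double the incidence easily passes; at n = 101 that holds only for very rare events, and with all 1389 cases it largely fails from 0.5% upward. A reader might also take the device to be the first of its kind. Section 14 says only that this device has not been marketed before, and Section 11 refers to similar devices already on the market.

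The gap itself remains. Section 11 makes acceptability depend on these parameters, the general language of Stage 3 sets no bound or denominator for them, and the condition on serious complications covers only serious events and has no bound of its own. The pooled denominator is also generous, since it includes colorectal and cardiomyopathy cases outside the valvular indication.

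**Conclusion.** The point holds in a limited form. The comparative measure for three safety rows is a no-worse-than claim that cannot be tested as written, because reference incidence, denominator, margin and confidence bound are all absent from both documents. That part rests on no assumption.

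Its size does. Under the literal point-estimate reading, the chance of missing a doubling with 101 cases runs from 82% at an assumed 0.1% to 5% at 5%. With all 1389 cases counted as exposures it runs from 23.5% at 0.1% to 1.5% or less from 0.5%. Table 1 expects a low incidence, which points towards the weaker end of the range, but the plan gives no number to settle it. It should be corrected, but it does not show that the safety evaluation as a whole fails.

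**What to change.** In the three Table 1 rows and the second bullet of the closing benefit-risk list in Section 11, replace the bare comparison with:
- the observed incidence and its denominator, defined as patient cases processed in actual use with incident ascertainment over a stated period;
- a one-sided 95% exact upper confidence bound;
- the documented incidence for similar devices and its source.

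Conclude *not higher* only if the bound lies below a limit justified in the risk management file before data are read. Otherwise report *not yet established, upper bound x%* (2.9% for 0/101) and carry the row into the PMS and PMCF already planned in Section 14.

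The limit is for the sponsor to justify. Purely as an illustration, for a limit of twice the documented incidence the zero-event minimum is the smallest n with n ≥ ln(0.05)/ln(1 − 2·p0):

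| p0 | Zero-event minimum | Chance an equally safe device passes, (1 − p0)^n | Uses for an 80% chance |
|---|---|---|---|
| 0.5% | 299 | 22% | about 1,945 |
| 1% | 149 | 22% | about 970 |
| 2% | 74 | 22% | about 452 |

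The minimums are therefore not adequate planning targets. Under such a rule a true doubling would pass at most 5% of the time at any n.

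The cost is a wording change, one exact bound per risk, and a defined way of counting uses and incidents. No pre-market patients are added, although the post-market denominator may need to be large if the documented incidence is low. The downside is a less favourable comparative safety statement before marketing.
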